### 3.3 Exclusion Criteria

Patients meeting any of the following criteria are excluded from the study:

1. Patients receiving any other standard or investigational agents are ineligible.
2. Patients with history or current evidence of the following conditions are excluded: neuromuscular disorder with associated elevated CK (e.g. inflammatory myopathies, muscular dystrophy, amyotrophic lateral sclerosis, spinal muscular atrophy), pancreatitis, retinal vein occlusion, uncontrolled HIV, or Hepatitis B/C. An exception will be made for (HIV)-infected patients on effective anti-retroviral therapy with undetectable viral load within 6 months and for subjects with cleared HBV and HCV infections, who may enroll in the study.
3. Known hypersensitivity or contraindication to any component of binimetinib or encorafenib or their excipients
4. Current use of a prohibited medication (including herbal medications, supplements, or foods), as described in Section [4.4](#), or use of a prohibited medication  $\leq 7$  days prior to the start of study treatment.
5. Patient has not recovered to  $\leq$  Grade 1 non-hematologic toxic effects of prior therapy before starting study treatment. **Note:** Stable chronic conditions ( $\leq$  Grade 2) that are not expected to resolve (such as neuropathy, myalgia, alopecia, prior therapy-related endocrinopathies) are exceptions and may enroll.

6. Impaired cardiovascular function or clinically significant cardiovascular disease including, but not limited to, any of the following:
  - History of acute coronary syndromes (including myocardial infarction, unstable angina, coronary artery bypass grafting, coronary angioplasty or stenting)  $\leq$  180 days prior to start date;
  - Congestive heart failure requiring treatment (New York Heart Association Grade  $\geq$  2);
  - Left ventricular ejection fraction (LVEF)  $<$  50% as determined by MUGA or ECHO;
  - Uncontrolled hypertension defined as persistent systolic blood pressure  $\geq$  150 mmHg or diastolic blood pressure  $\geq$  100 mmHg despite current therapy;
  - History or presence of clinically significant cardiac arrhythmias (including resting bradycardia, uncontrolled atrial fibrillation or uncontrolled paroxysmal supraventricular tachycardia);
  - Triplicate average baseline QTc interval  $\geq$  480 ms.
7. Impairment of gastrointestinal function or disease which may significantly alter the absorption of study drug (e.g., active ulcerative disease, uncontrolled vomiting or diarrhea, malabsorption syndrome, small bowel resection with decreased intestinal absorption), or recent ( $\leq$  90 days) history of a partial or complete bowel obstruction, or other conditions that will interfere significantly with the absorption of oral drugs.
8. History of recent ( $\leq$  90 days) thromboembolic or cerebrovascular event such as transient ischemic attack, cerebrovascular accident, or hemodynamically significant (massive or sub-massive) deep vein thrombosis or pulmonary emboli (DVT/PE). *Note:* Patients with DVT/PE that does not result in hemodynamic instability may enroll as long as they are anticoagulated for at least 4 weeks. *Note:* Patients with DVT/PE related to indwelling catheters or other procedures may enroll.
9. Patients with uncontrolled intercurrent illness including, but not limited to, ongoing or active infection or psychiatric illness/social situations that would limit compliance with study requirements, are ineligible.
10. Pregnant women are excluded from this study because the effects of encorafenib and/or binimetinib on a fetus are unknown. Because there is an unknown but potential risk for adverse events in nursing infants secondary to treatment of the mother with encorafenib or binimetinib, breastfeeding should be discontinued if the mother is treated with encorafenib and/or binimetinib.
11. Patients who previously received BRAF or MEK inhibitors are excluded (including but not limited to dabrafenib, vemurafenib, encorafenib, sorafenib, trametinib, binimetinib, cobimetinib, or selumetinib).
12. Patients will be excluded if their tumor harbors a known RAS activating mutation. This does not need to be specifically tested for eligibility.

### **3.4 Additional Inclusion Criteria for Surgical Arm**

Patients must meet the above inclusion / exclusion criteria for consideration with one exception. Patients with a BRAF-V600 E or K mutated low-grade glioma for whom there is a strong clinical suspicion of progression to high-grade would also be eligible for this arm. Additionally:

1. Patients must have a clinical indication for a tumor surgery.
2. No *a priori* contraindication to biospecimen collection (blood, tumor, CSF).

### **4.0 TREATMENT PLAN**

This is a Phase II, open-label, multicenter efficacy study of encorafenib in combination with binimetinib in adult patients with recurrent BRAF-V600E/K mutated high-grade primary brain tumors. The goal of this study is to estimate the efficacy of encorafenib and binimetinib as measured by radiographic response in recurrent high-grade primary brain tumors.

[figure not shown]
There are two arms: medical and surgical. All subjects on the medical arm must have histologically confirmed high-grade glioma (including but not limited to glioblastoma (GBM), anaplastic astrocytoma (AA), and gliosarcoma), anaplastic pleomorphic xanthoastrocytoma (aPXA) or other high-grade primary brain tumor (including but not limited to anaplastic ganglioglioma (AG), and anaplastic ependymoma) that is recurrent after first-line treatment. Subjects on the surgical arm must have a high-grade glioma or a known BRAF-mutated low-grade glioma with high clinical suspicion for progression to high-grade.

## 4.1 Treatment Schema

### Medical Arm Treatment Schema

Following enrollment, patients will receive encorafenib and binimetinib at the FDA-approved dose of 450 mg of encorafenib once daily and the FDA-approved dose of 45 mg of binimetinib twice daily separated by 12 hours, continuously in 28-day cycles until progression or unacceptable toxicity. Patients will be followed by routine blood work, and general and neurological examination. A brain MRI will be performed prior to every odd-numbered cycle (every 8 weeks). Response will be assessed by RANO criteria (Section 8.1). Patients may remain on study and receive treatment until progression or as otherwise determined in Section 10.1.

[figure not shown]

## Surgical Arm Treatment Schema

Subjects in the surgical cohort must be candidates for a clinically-indicated surgery and must have a BRAF V600E/K-mutated high-grade glioma or a low-grade glioma with high clinical suspicion for progression to high-grade. These subjects will take encorafenib and binimetinib in combination at their FDA-approved doses (see Section 4.3 for administration details) for 10-14 days prior to surgery, with a preference for 14 days, though a minimum of 10 days is acceptable. The last dose of both drugs will be administered two hours prior to surgery. Specimens will be collected as described in Section 9.6 and processed as described in the **Laboratory Manual**.

After surgery, the subjects will not take further encorafenib or binimetinib until a study visit to assess their neurological exam, physical exam (or telemedicine physical evaluation), and performance status, at 2-6 weeks post-operatively. At time of restarting combination treatment, subjects will follow the schedule listed above for the medical cohort, and will continue treatment as defined in Section 10.1.

Patients with histopathology inconsistent with high-grade glioma (either treatment effect or low grade glioma) will be replaced. Overall survival will be assessed from the first day that patient receives drug to death from any cause.

## **Required Ophthalmology Exam for the Medical and Surgical Arms**

A full ophthalmic examination will be performed by an ophthalmologist at Screening, and include best corrected visual acuity, slit lamp examination, intraocular pressure, dilated fundoscopy and Ocular Coherence Tomography (OCT). Examination of the retina is required, especially to identify findings associated with serous retinopathy and RVO. On study, patients receiving binimetinib should be assessed at every physical examination for decreased visual acuity using a gross perimetry test (as opposed to automated visual field testing) in person or by telemedicine evaluation. Symptomatic patients should be referred for a full ophthalmic consultation.

- For patients with clinical suspicion of retinal abnormalities of any grade (e.g., serous retinopathy, RVO, photopsia, metamorphopsia, impairment of visual acuity), these additional assessments should be mandatory:

Non-vascular abnormalities: spectral domain OCT recommended  
Vascular abnormalities: fluorescein angiography of the central 30 degrees.

### **4.2 Treatment Requirements for subsequent cycles**

If patients do not meet stopping criteria for encorafenib or binimetinib, and their study drugs are not being held based on their adverse events (per CTCAE version 5.0 defined in Section [5.1](#)), they will proceed with the next cycle.

### **4.3 Encorafenib and Binimetinib Administration**

Encorafenib will be administered in combination with binimetinib using the FDA approved doses. The dose of encorafenib is 450 mg orally once daily, taken with binimetinib. The dose of binimetinib is 45 mg orally twice daily, taken approximately 12 hours apart. It is recommended that both study drugs be taken in the morning rather than the evening. The study drugs may be taken with or without a meal.

Medical Arm patients: Encorafenib and binimetinib are taken every day for each 28 day cycle.

Surgical Arm patients: Encorafenib and binimetinib are taken for 10-14 days prior to surgery (preferably 14 days, though a minimum of 10 days is acceptable). The last dose of both drugs will be taken two hours prior to surgery. Following recovery from surgical resection (2-6 weeks), encorafenib and binimetinib are taken every day for each 28 day cycle.

If a subject vomits after taking study medication, the subject should be instructed not to retake the dose and should take the next dose as originally scheduled.

If a subject misses a dose of binimetinib, the subject may take the dose immediately if the next dose is scheduled for at least 6 hours later. If the next scheduled dose of binimetinib

is due in less than 6 hours, the subject should skip the dose and resume binimetinib dosing at the next scheduled dose.

If a subject misses a dose of encorafenib, the subject may take the dose immediately if the next dose is scheduled for at least 12 hours later. If the next scheduled dose of encorafenib is due in less than 12 hours, the subject should skip the dose and resume encorafenib dosing at the next scheduled dose.

Treatment will generally be administered on an outpatient basis. Patients will be provided with medication diaries ([Appendix I-IV](#)) and instructed in their use. Patients will be instructed to bring all unused medication and their diaries to each study visit for assessment of compliance.

Because study treatment is intended for self-administration, if coming to the clinic presents a safety risk, it is permitted to ship the study drug and the appropriate medication diaries to the patient's residence before the scheduled cycle Day 1. The study drug should be shipped by a secure delivery method with package tracking and a delivery confirmation. The regulatory requirements for maintaining investigational product remain and should be addressed and documented.

No investigational or commercial agents or therapies other than those described below may be administered with the intent to treat the patient's malignancy.

#### **4.4 General Concomitant Medication and Supportive Care Guidelines**

##### **4.4.1 Permitted Concomitant Therapy Requiring Caution and/or Action**

Encorafenib has been identified in vitro to be metabolized by CYP3A4 and to a lesser extent by CYP2C19. Concomitant use of moderate CYP3A4 inhibitors while on study should be avoided. If use of moderate CYP3A4 inhibitors is unavoidable and no alternatives are available, short-term use ( $\leq 30$  days) is permitted with accompanying dose reduction to one-half of the encorafenib dose prior to use of moderate CYP3A4 inhibitors (or as close as can be achieved without exceeding the target dose). The encorafenib dose that was taken prior to initiating the CYP3A4 inhibitor may be resumed after the inhibitor has been discontinued for 3 to 5 elimination half-lives. Strong inhibitors of CYP2C19 should be used with caution when co-administered with encorafenib.

Encorafenib is a reversible inhibitor of CYP1A2, CYP2B6, CYP2C8, CYP2C9, CYP3A4 and UGT1A1. It is also a time-dependent inhibitor of CYP3A4, and induced CYP2B6, CYP2C9 and CYP3A4 in human primary hepatocytes. Permitted medications to be used with caution in this study include those that are sensitive substrates of CYP1A2, CYP2B6, CYP2C9, CYP2C9, CYP3A4, and UGT1A1 or those substrates that have a narrow therapeutic index.

There is a potential for encorafenib to induce CYP3A4, which may reduce the effectiveness of hormonal contraception methods. Therefore, the use of at least 1 form of non-hormonal

contraception is required for females of childbearing potential during participation in this study. Caution should be used in participants receiving concomitant treatment with other drugs that are substrates of CYP3A4 as the efficacy of these drugs could be reduced when administered with encorafenib.

*In vitro* data showed that encorafenib is a substrate of the transporter P-gp. Thus, drugs that are known to inhibit or induce P-gp should be used with caution. Encorafenib is also a potent inhibitor of the renal transporters, OAT1, OAT3 and OCT2, and the hepatic transporters OATP1B1 and OATP1B3. The co-administration of drugs that are known to be sensitive or narrow therapeutic index substrates of OAT1, OAT3, OCT2, OATP1B1 or OATP1B3 should be used with caution.

*In vitro*, binimetinib has been identified to be primarily metabolized by glucuronidation through UGT1A1. Binimetinib has also been shown to be a substrate of P-gp and BCRP. It is advised that inhibitors and inducers of UGT1A1, P-gp or BCRP transporters should be taken with caution when co-administered with binimetinib.

For a listing of examples of substrates, inhibitors and inducers to be used with caution, please consult with the FDA website: [Drug Development and Drug Interactions: Table of Substrates, Inhibitors and Inducers](#). Note that this list is not exhaustive.

Investigators should use caution when administering encorafenib or binimetinib with concomitant medications with a known, conditional or possible risk to prolong the QT interval and/or induce TdP. Subjects receiving such medications must be carefully monitored for potentiation of toxicity due to any individual concomitant medication, and may require dose titration of the concomitant medication. See the CredibleMeds® website for examples: [Combined List of Drugs That Prolong QT and/or cause Torsades de Pointes \(TDP\)](#). Note that this list is not exhaustive.

#### **4.4.2 Prohibited Concomitant Medications During Study**

Patients may receive other medications that the investigator deems to be medically necessary, with the specific exception of non-protocol specified chemotherapy, radiotherapy, anti-neoplastic biological therapy or other investigational agents. Patients who require the use of any of the aforementioned treatments for clinical management should be removed from the study.

Per FDA labeling, administration of encorafenib along with a strong or moderate CYP3A4 inhibitor increases encorafenib plasma concentrations and may increase adverse reactions. The use of strong inhibitors of CYP3A4 is prohibited. Concomitant administration of encorafenib with a strong or moderate CYP3A4 inducer may decrease encorafenib plasma concentrations and decrease encorafenib efficacy. Use of moderate and strong inducers of CYP3A4 is prohibited. Similarly, concomitant administration of encorafenib with sensitive CYP3A4 substrates may result in increased toxicity or decreased efficacy. Specifically, co-administration of encorafenib with hormonal contraceptives (CYP3A4 substrates) can result in decreased concentrations and loss of hormonal contraceptive efficacy. Avoid

hormonal contraceptives.

The Principal Investigator should be alerted if the patient is taking any agent known to affect or with the potential for drug interactions. The study team should check a frequently-updated medical reference for a list of drugs to avoid or minimize use thereof.

#### **4.4.3 Corticosteroids**

The lowest required corticosteroid dose should be maintained throughout the duration of the study in order to eliminate steroid effects as a confounding variable in the interpretation of serial brain imaging studies. Corticosteroid doses can be tapered as clinically indicated if the patient appears to be responding to therapy as judged by serial scans. Alternatively, corticosteroid dose may be increased in the event of clinical deterioration or at the discretion of the attending physician. In the event of suspected clinical deterioration, repeat brain imaging is recommended.

#### **4.4.4 Herbal and Non-Traditional Medications**

No data exist regarding the interaction of encorafenib and binimetinib with commonly used herbal or non-traditional medications. Patients should be instructed not to use such medications while receiving encorafenib and binimetinib therapy.

### **4.5 Lifestyle Considerations**

#### **4.5.1 Contraception**

Female participants of childbearing potential must agree to take appropriate precautions to avoid pregnancy from Screening through 30 days after the last dose of study drug/treatment. In addition, female participants must refrain from donating ova during the study through 30 days after the end of systemic exposure of study drug/treatment. Male participants should use a condom during treatment and through 90 days after the end of systemic exposure to study drug/treatment. If the male participant has a partner that is of child-bearing potential, the partner should also use contraception through 90 days after the end of systemic exposure to study drug/treatment. In addition, male participants must refrain from donating sperm during the study through 90 days after the end of systemic exposure of study drug/treatment. Males who have had a vasectomy qualify as having met the requirement for a highly effective birth control method.

#### **Definitions:**

##### **Woman of Childbearing Potential (WOCBP)**

A woman is considered fertile following menarche and until becoming post-menopausal unless permanently sterile (see below). If fertility is unclear (e.g., amenorrhea in adolescents or athletes) and a menstrual cycle cannot be confirmed before first dose of study treatment, additional evaluation should be considered.

Women in the following categories are **not** considered WOCBP

1. Premenarchal
2. Premenopausal female with 1 of the following:
  - Documented hysterectomy
  - Documented bilateral salpingectomy

- Documented bilateral oophorectomy  
For individuals with permanent infertility due to an alternate medical cause other than the above, (e.g., mullerian agenesis, androgen insensitivity), Investigator discretion should be applied to determining study entry.  
*Note:* Documentation can come from the site personnel's: review of the participant's medical records, medical examination, or medical history interview.
3. Postmenopausal female
- A postmenopausal state is defined as no menses for 12 months without an alternative medical cause.
  - A high follicle stimulating hormone (FSH) level in the postmenopausal range may be used to confirm a postmenopausal state in women not using hormonal contraception or hormonal replacement therapy (HRT). However, in the absence of 12 months of amenorrhea, confirmation with more than one FSH measurement is required.
  - Females on HRT and whose menopausal status is in doubt will be required to use one of the non-estrogen hormonal highly effective contraception methods if they wish to continue their HRT during the study. Otherwise, they must discontinue HRT to allow confirmation of postmenopausal status before study enrollment.

#### 4.5.2 Contraception Guidance:

**NOTE: There is a potential for encorafenib to induce CYP3A4, which may reduce the effectiveness of hormonal contraception methods. Therefore, the use of at least 1 form of non-hormonal contraception is required for females of childbearing potential during participation in this study.**

The contraception guidelines outlined below are adapted from the recommendations related to contraception and pregnancy testing in clinical trials [guidance document \(Clinical Trials Facilitation Group Guidelines 2014\)](#). Participants must agree to use highly effective methods of contraception if it is mandated locally or when, in the judgment of the Investigator, compliance with acceptable methods is likely to be suboptimal.

The following methods have been classified as being highly effective (i.e., failure rate < 1% per year when used consistently and correctly) in preventing a pregnancy:

- Complete abstinence from heterosexual intercourse during the entire period of risk associated with the study treatments; the reliability of sexual abstinence should be evaluated in relation to the duration of the clinical trial and the preferred and usual lifestyle of the participant
- Combined (estrogen and progestogen containing) hormonal contraception associated with inhibition of ovulation:
  - Oral
  - Intravaginal
  - Transdermal
- Progestogen-only hormonal contraception associated with inhibition of ovulation:
  - Oral
  - Injectable
  - Implantable
- Intrauterine device (IUD)
- Intrauterine hormone-releasing system (IUS)
- Bilateral tubal occlusion
- Vasectomised partner (considered highly effective provided the vasectomized male has received medical assessment of surgical success and that the male is a female participant's sole sexual partner)

Acceptable birth control methods characterized as having a failure rate of more than 1% per year include:

- Progestogen-only oral hormonal contraception, where inhibition of ovulation is not the primary mode of action
- Male or female condom with or without spermicide
- Cap, diaphragm or sponge with spermicide

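### Section 4.5.2 lets systemic hormonal contraception count as highly effective for women taking encorafenib, although section 4.4.2 says encorafenib can undo its effect

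*Combined protocol and SAP*

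**What the plan says.** Section 4.5.2 opens with a bold NOTE on the CYP3A4 interaction: "Therefore, the use of at least 1 form of non-hormonal contraception is required for females of childbearing potential during participation in this study". It then sets two tiers.

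- **Stricter tier.** It is conditional: "Participants must agree to use highly effective methods of contraception if it is mandated locally or when, in the judgment of the Investigator", compliance with merely acceptable methods is likely to be poor. The list begins: "The following methods have been classified as being highly effective (i.e., failure rate < 1% per year when used consistently and correctly". Two of its entries are systemic hormonal methods: "Combined (estrogen and progestogen containing) hormonal contraception associated with inhibition of ovulation" and "Progestogen-only hormonal contraception associated with inhibition of ovulation". Neither carries a qualifier for women on study drug.
- **Lower tier.** These methods have failure rates above 1% per year. They include "Male or female condom with or without spermicide".

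Other sections bear on the same question:

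- Section 4.4.2, under its heading on prohibited medications, says that taking encorafenib with hormonal contraceptives can lower their concentrations and make them ineffective. It tells sites to avoid them.
- Section 4.4.1 repeats the requirement for at least one non-hormonal method.
- Inclusion criterion 9 (section 3.2) defines adequate contraception for women of childbearing potential as an IUD, a barrier, another non-hormonal method, or abstinence.
- The definitions in section 4.5.1 cover women on HRT whose menopausal status is uncertain. To continue HRT they must use a highly effective method described as non-estrogen hormonal. The stated alternative is to stop HRT.
- Section 4.5.1 also covers male participants. If the partner is of childbearing potential, "the partner should also use contraception through 90 days after the end of systemic exposure to study drug/treatment".

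**The concern.** The stricter tier exists for situations where an ordinary method is judged insufficient. For a woman taking encorafenib, its below-1% standard can be credited to a method that another section of the same protocol says may stop working. The back-up method that the NOTE requires need not meet that standard. Where the tier is triggered by doubt about compliance with acceptable methods, the back-up may be one of the methods in doubt.

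What is at stake is participant safety and consistency between sections. Exclusion criterion 10 describes the fetal effects of both drugs as unknown. Table 9.1 schedules a serum pregnancy test at baseline only, so prevention during treatment rests largely on contraception.

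**Working it through.** The plan gives no figure to reproduce and no arithmetic applies. The check is whether the sections, taken together, let the stricter tier be met without a reliably highly effective method.

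1. **Does the tier reach women on encorafenib?** Yes. It is addressed to participants generally, and the 4.5.2 NOTE concerns women of childbearing potential in the study.
2. **What satisfies the tier on its face?** Any listed method. Combined and progestogen-only hormonal methods are listed without exception.
3. **What does the NOTE add?** At least one non-hormonal method. It does not say from which tier, and it does not remove hormonal methods from the stricter list.
4. **Test case: combined pill plus condom.** The pill is a listed method, so the tier is met. The condom is non-hormonal, so the NOTE and section 4.4.1 are met. A barrier method also meets inclusion criterion 9.
5. **Apply section 4.4.2 to the test case.** The pill may lose its effect. What is then left is the condom, which 4.5.2 itself rates above 1% per year. A site that followed 4.4.2 would not use the pill, but 4.5.2 does not refer to 4.4.2.
6. **Is the list itself wrong?** No. Partners of male participants do not take encorafenib, so the hormonal entries remain sound for them. Section 4.5.1 also applies the notion of a highly effective method to men: "Males who have had a vasectomy qualify as having met the requirement for a highly effective birth control method".
7. **The HRT wording.** *Non-estrogen hormonal highly effective* has two readings. It can mean a hormonal method without estrogen, that is, a progestogen-only method, which is in the class section 4.4.2 warns about. It can also mean any highly effective method not based on estrogen. The text does not settle which.

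The tier can therefore be met on the wording of 4.5.2 by a combination whose only listed highly effective component is one that 4.4.2 says to avoid.

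**The case against.** The strongest reply is that the protocol already deals with the interaction in four places. Inclusion criterion 9, section 4.4.1 and the NOTE each call for a non-hormonal method, and section 4.4.2 says to avoid hormonal contraceptives. Sites are bound by the whole protocol, so the gap appears only when 4.5.2 is read in isolation. The list is a general classification adapted from a named guidance document, with the drug-specific caution placed directly above it. The route to harm is narrow: the tier must apply, and the site must then accept a hormonal method despite 4.4.2. If 4.4.2 is a strict prohibition, exclusion criterion 4 would also bar current users at screening.

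Most of this stands, and it is why the point is minor. It does not remove the inconsistency. The NOTE and 4.4.1 ask for at least one non-hormonal form, which reads as an addition to a hormonal method and not a replacement. Section 4.4.2 says avoid, and the documents do not settle whether that amounts to a prohibition. A site working from the section headed as contraception guidance would find the pill listed as qualifying.

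Two stronger readings are tempting, and neither is supported. A reader might infer that the protocol lets a woman on encorafenib rely on a hormonal method alone; inclusion criterion 9, 4.4.1 and the NOTE rule that out. A reader might also infer that a pill plus a condom fails the 1% standard. The documents give no failure rate for that combination under encorafenib, so they leave the standard unassured, not breached.

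**Conclusion.** The point holds as a minor inconsistency between sections 4.5.2 and 4.4.2, together with an ambiguous HRT rule in 4.5.1. The textual finding is firm; its practical consequence is limited and cannot be quantified. The documents do not give the number of women in the stricter tier or continuing HRT, and they name no local mandate. The conclusion assumes that a site may read 4.5.2 on its own terms; a site that treats 4.4.2 as a strict prohibition would already avoid the problem. Outside the conditional tier, inclusion criterion 9 accepts a barrier method alone, and that standard is not challenged here. Endpoints, sample size and analyses are unaffected.

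**What to change.** 1. Keep the 4.5.2 list as it stands, because it remains valid for partners of male participants.
2. Add to 4.5.2: *For female participants of childbearing potential taking encorafenib, systemic hormonal methods do not count as highly effective. Where this tier applies, a non-hormonal listed method is needed: abstinence, IUD, bilateral tubal occlusion or a vasectomised partner.*
3. In the 4.5.1 definitions, change *non-estrogen hormonal* to *non-hormonal*, keeping the option to stop HRT.

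All four named methods already satisfy inclusion criterion 9, so that criterion needs no change. The sponsor could also state whether the hormone-releasing intrauterine system counts, and whether current hormonal users are excluded or may enroll with a non-hormonal method added. Those are optional clarifications, not corrections.

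The cost is one addition to 4.5.2, one wording change in 4.5.1 and a check that the consent form matches. No procedure is added. The downside is a slightly narrower choice for the few women in this tier or continuing HRT; partners of male participants lose no option.
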